9.5. Recording and Reporting SUSARs

All SARs or suspected SARs occurring during this trial must be reported by site to NCTU immediately (and no later than 24 hours of the site becoming aware of the event), through the provided SAE/SAR reporting method. This will automatically be distributed to the Sponsor and CI.

The assessment of expectedness will be performed by the CI on behalf of the Sponsor against the approved Reference Safety Information (RSI) for the trial. The RSI is contained within the approved SMPCs for the trial's IMPs (see section 8.1) and is detailed here.

Medication	Section 4.8 of the SmPC
Gabapentin	Neurontin 100mg Hard Capsules
Amitriptyline	Amitriptyline 10mg Film-Coated Tablets
Lidocaine 2%	Lidocaine Hydrochloride Injection BP 2% w/v
Botox	BOTOX 100 Allergan Units Powder for solution for injection

Where the CI is unavailable, another medically or dentally qualified individual may be delegated this task via the trial delegation log.

All SUSARs occurring during the trial must be reported to the MHRA and REC. The Sponsor will perform this reporting. Fatal and life-threatening SUSARS must be reported no later than 7 calendar days after the Sponsor has first knowledge of the event. Any relevant follow-up information must be sought and reported within a further 8 calendar days.

Non-life threatening SUSARs must be reported to the MHRA no later than 15 calendar days after the Sponsor has first knowledge of the event. Any relevant follow-up information should be sought and reported as soon as possible after the initial report.

NCTU will be responsible for ensuring that the CI undertakes the expectedness assessment to determine if a SAR is unexpected and requires reporting as a SUSAR. The reporting timeframe starts at day 0 when the Sponsor is in receipt of a minimum set of information:

- Sponsor trial reference and trial name (sponsor reference)
- EudraCT number
- Patient trial number
- Name of IMP(s)
- Date of notification of the event
- Medical description of the event
- Date of the onset of the event (including time of onset and end date if applicable)
- Causality assessment
- Seriousness of the event, particularly if life threatening or fatal
- An identifiable reporter (e.g., Principal Investigator)

This information must be provided on a SUSAR Reporting Form. The site is expected to fully cooperate with the NCTU in order that a full and detailed report can be submitted to the MHRA and REC within the required timelines.

PIs will be informed of all SUSARs by NCTU.

9.6. Responsibilities

Principal Investigator

- Checking for AEs and ARs when participants attend for treatment or follow-up.
- Using clinical judgement in assigning seriousness and causality of adverse events.
- Ensuring that all SAEs and SARs, including SUSARs, are recorded and reported to the Sponsor within 24 hours of becoming aware of the event and provide further follow-up information as soon as available.
- Ensuring that AEs and ARs are recorded and reported to the Sponsor in line with the requirements of the protocol.
- Ensuring all AEs are recorded in eCRF.

Chief Investigator

- Clinical oversight of the safety of trial participants, including an ongoing review of the risk/benefit.
- Using clinical judgement in assigning seriousness and causality assessments for SAEs where it has not been possible to obtain local medical assessment.
- Provide review of assessment of causality of all SAEs on behalf of Sponsor (where the assessment was not originally performed by the CI).
- Using clinical judgement in assigning expectedness to SARs in line with the RSI and following the principals of GCP.
- Immediate review of all SUSARs.
- Review of specific SAEs and SARs in accordance with the trial risk assessment and protocol.
- Review/assignment of Medical Dictionary for Regulatory Activities (MedDRA) or body system coding for all SAEs and SARs.
- Preparing the clinical sections and final sign off of the Development Safety Update Report (DSUR).

Sponsor

- Data collection and verification of AEs, ARs, SAEs, SARs and SUSARs onto a database (may be delegated to CTU).
- Reporting safety information to the independent oversight committees for the ongoing assessment of the risk/benefit ratio throughout the life of the trial (may be delegated to NCTU).
- Assessment of expectedness of any SUSARs (may be delegated to the CI)
- Expedited reporting of SUSARs to the MHRA and REC within required timelines
- Notification of all investigator sites of any SUSAR that occurs (may be
- delegated to NCTU)
- Reviewing RSI at least annually and notification of PIs of any required updates (may be delegated to NCTU).

- Preparing tables and other relevant information for the DSUR in collaboration with the CI and ensuing timely submission to the MHRA and REC (may be delegated to NCTU)

TSC/DMC/TOC

- Review of safety data collected to date to identify any concerns

9.7. Notification of Deaths

Fatal SUSARs will be reported within 7 days to REC and MHRA. Monitoring of all other deaths will occur via the TMG, IDMC and the TSC.

All participant deaths will need to be reported as SAEs, with the reason for death identified on the SAE form and recorded in the eCRF.

9.8. Pregnancy Reporting

In the event of a trial participant or the partner of a trial participant becoming pregnant on the trial, the site must notify NCTU, the Chief Investigator and the sponsor representative within 24 hours of becoming aware of the pregnancy. This is by completion of a pregnancy reporting form which should be sent to [contact].

Site must approach the trial participant or the partner of a trial participant to obtain consent to follow the pregnancy to completion. The outcome of the pregnancy will then be obtained when available.

Pregnancy in itself is not an SAE. In the event that a congenital anomaly or birth defect does occur, this must be reported as an SAE.

9.9. Overdose

A toxic overdose, whether intentional or accidental must be reported immediately to NCTU and patients should be directed or escorted (if on premises) to their local emergency department. Toxbase can be consulted on toxic doses in adults: ≥3mg/kg of amitriptyline or symptomatic at a lower overdose; ≥150mg/kg Gabapentin or symptomatic at a lower overdose; ≥6mg/kg lidocaine or symptomatic at a lower overdose; Botox overdose is a relative term and is described in section 4.9 of its SmPC. Whilst it is not in itself an adverse event or serious adverse event, any untoward medical occurrence as a result of an overdose, or any condition that leads to an overdose being taken is considered an AE or SAE and should be reported as per section 9.2. Details of the event must be recorded in the eCRF and participant's medical records.

9.10. Reporting Urgent Safety Measures

An Urgent Safety Measure (USM) is an action that the Sponsor or an Investigator may take in order to protect the subjects of a trial against any immediate hazard to their health or safety. Upon implementation of an USM by an Investigator, the Sponsor, CI and NCTU] must be notified immediately and details of the USM given. The Sponsor must inform the MHRA and the NHS REC within 3 days of the USM taking place in accordance with the Sponsor's standard operating procedures.

The MHRA may alert the trial team to any new safety signals identified for the trial IMPs. In the event of this occurring, the IMP may need to be discontinued with immediate effect.

9.11. Development Safety Update Reports

The following reports will be submitted each year as a condition of the authorisation to undertake a clinical trial or as a condition of a favourable opinion from a REC.

In the UK, a Development Safety Update Report (DSUR) will be submitted to the MHRA and NHS REC once a year on the date of CTA approval of the trial. NCTU must ensure that the report is submitted within 60 days of the end of the reporting period. The Trial Management Group must contribute to the compilation of the DSUR with the CI being involved in completion of the relevant sections requiring medical input and assessment of any newly identified risks and the summary of benefit-risk considerations. The CI must review and authorise the final report before it is ready for submission. The DSUR should also be reviewed by the NCTU QA Manager and Sponsor Representative prior to submission. NCTU staff will prepare and submit DSURs for the trial, in accordance with NCTU SOPs.

An NRES CTIMP Safety Report Form will be sent to REC along with the DSUR. Reports of SUSARs in the UK, urgent safety measures and any other safety reports submitted, for example, reports of an independent data monitoring committee (IDMC), will also be accompanied by a Safety Report Form.

A NRES Annual Progress Report for CTIMPs will be prepared and submitted by the CI to REC, and copied to Sponsor, on the anniversary date of the REC favourable opinion.

10. STATISTICAL CONSIDERATIONS

10.1. Analysis Populations

Intention-to-treat (ITT): This population contains all participants randomised into the trial who participated in at least one post-baseline assessment, analysed according to randomised treatment allocation.

Safety Population (SP): This population contains all participants who received **any** trial treatment, analysed according to randomised treatment allocation.

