2. RATIONALE

It is critical to generate some robust data on the effectiveness and cost-effectiveness of injectable treatments (BTX and lidocaine) given recent UK data demonstrate they are already being used as (part of) routine clinical care for M-TMD in a substantial number of secondary care settings. The lack of robust data on BTX's effectiveness, dose scheduling, and risks in M-TMD are apparent in the variability of the responses on dosing, scheduling, and administration from those clinical units in the UK utilising it (Anwar et al., 2022). Lidocaine is known to be an active comparator treatment delivered by the same

mode of administration as BTX and may offer a more effective or cost-effective treatment option (Machado et al., 2018)

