3.2. Secondary Objective(s)

- a) To assess cost-effectiveness in terms of incremental cost per QALY over a lifetime horizon.
- b) To evaluate whether the interventions affect generic quality of life (EQ-5D-5L).
- c) To examine responder rates and adherence over time in all interventions.
- d) To evaluate whether any of the interventions affect jaw function.
- e) To evaluate whether any of the interventions affect psychosocial distress, sleep quality, or analgesia use.
- f) To compare the adverse effect profiles of the interventions including the MRI sub study examining changes in the temporomandibular joint.
- g) To explore treatment experiences and acceptability of interventions.

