7.6. Discontinuation of trial treatment

Participants may elect (or investigators may elect for participants) to stop receiving any of the IMPs and remain on the trial. Participants will continue to take part in trial assessments as per the schedule of events except for the MRI sub-study if they are enrolled in this. After discontinuation, if they elect to begin a new therapy for TMD within routine clinical care (NHS or private), they will be asked to complete the next set of research assessments that are due prior to beginning the new treatment and then go back to the regular schedule following this and the new treatment details recorded in their clinical notes and CRF.

Discontinuation of treatment along with a reason, if possible, will be recorded in the clinical notes and the CRF. A discontinuation from treatment form will also be completed and stored in the ISF.

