10.2.2. Analysis of Secondary Outcome Measures

Secondary outcomes will be analysed for superiority of each intervention against TAU. All analyses will be in the ITT population i.e. following a treatment policy approach. Estimated differences between treatment groups will be reported with two-sided 95% confidence intervals.

Secondary patient-reported outcomes (PHQ-4, BPSQI, SF-JFLS, GIC, Liverpool adverse effects profile, FaCE) will be analysed using linear mixed effects regression models similar to the co-primary outcomes above, but with the baseline value of the corresponding outcome included as a fixed effect. Domains or individual items may also be reported and analysed using appropriate regression techniques as described in the SAP. Analgesia use at any time during the trial will be analysed as a binary outcome using mixed effects logistic regression with a random effect for site and fixed effects for treatment and the stratification factor of psychosocial status. The secondary outcomes of 30% and 50% reduction from baseline in CPI and OHIP-TMD will be analysed separately at each timepoint using mixed effects logistic regression with a random effect for site and fixed effects for treatment, baseline score and the stratification factor of psychosocial status.

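### The Safety Population is entered by treatment received but grouped by randomised arm, which dilutes between-drug adverse-event differences if anyone receives another arm's drug

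*Protocol*

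**What the plan says.** Section 10.1 of the protocol defines two populations. The ITT population is everyone randomised "who participated in at least one post-baseline assessment, analysed according to randomised treatment allocation". The Safety Population is everyone who received any "trial treatment, analysed according to randomised treatment allocation". The entry conditions differ; the grouping rule is the same.

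Section 3.2, objective (f), is "To compare the adverse effect profiles of the interventions including the MRI sub study examining changes in the temporomandibular joint". For secondary outcomes, among which section 10.2.2 lists the Liverpool adverse effects profile, that section states: "All analyses will be in the ITT population i.e. following a treatment policy approach". Section 10 does not mention the Safety Population again after 10.1, and no part of the protocol describes a comparison of harms by treatment received.

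On departures from allocation, section 7.6 says: "Participants may elect (or investigators may elect for participants) to stop receiving any of the IMPs and remain on the trial". It also lets such participants start a new TMD therapy in NHS or private care, with the details entered in the CRF. Section 2 says of the two injectables that "they are already being used as (part of) routine clinical care for M-TMD in a substantial number of secondary care settings".

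**The concern.** A safety population defined by exposure is normally meant to show what happened to people given each product. Here exposure decides only who is counted, and randomisation decides under which heading. Read literally, a participant allocated to TAU who took no tablets and received only a trial injection would enter because of the injection and be tabulated under TAU. A participant who stopped tablets and later received an injectable would have events from the injectable counted under TAU.

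Each such case moves an event from the drug given to another drug's column, so the arms look more alike than the drugs are. For efficacy in a superiority trial, this kind of dilution is conservative. For harms it works the other way, because it makes a real difference between products harder to see. Objective (f) asks about the interventions, and section 9.3 pre-specifies a product-linked event (facial weakness after Botox), so the comparative tables are where this would matter.

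**Working it through.** The point concerns a definition, so no stated figure turns on it. The arithmetic below only sizes the effect.

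**Arm size, from section 10.3.** SD 20.7, difference 6.0, two-sided 5%, power 90%: 251 per arm. Adjusting for the baseline correlation: 251 × (1 − 0.6²) = 160.6, so 161. Allowing for 27% loss: 161 / 0.73 = 220.5, so 221. Three arms: 3 × 221 = 663, as the protocol states.

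**Assumptions, because the protocol gives no figures.** Let c be the share of an arm that receives the other drug in place of its own; the range taken is 1% to 10%. Let p1 and p0 be the event rates on the two drugs; the illustrations are 10% versus 0% and 20% versus 5%.

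**One-way crossover** (for example TAU to an injectable, none back):
- rate tabulated under TAU = (1 − c)p0 + c·p1; rate under the injectable = p1
- by-allocation difference = (1 − c)(p1 − p0)

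At c = 5%, p1 = 10%, p0 = 0%: 0.05 × 221 = 11.05 participants; 11.05 × 0.10 = 1.1 events under TAU; the TAU rate is 0.5% instead of 0%; the difference is 10 × 0.95 = 9.5 points instead of 10.

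**Symmetric crossover** (share c in both directions):
- by-allocation difference = (1 − 2c)(p1 − p0)

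| c | Participants per arm of 221 | 10% v 0%, one-way | 10% v 0%, symmetric | 20% v 5%, one-way | 20% v 5%, symmetric |
|---|---|---|---|---|---|
| 0% | 0 | 10.0 | 10.0 | 15.0 | 15.0 |
| 1% | 2.2 | 9.9 | 9.8 | 14.85 | 14.7 |
| 5% | 11.05 | 9.5 | 9.0 | 14.25 | 13.5 |
| 10% | 22.1 | 9.0 | 8.0 | 13.5 | 12.0 |

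Differences are in percentage points. The one-way column is closer to the route the protocol leaves open, which is a switch after stopping trial treatment; the symmetric column is the less favourable case. The c = 0% row shows that the choice of grouping has no effect when nobody crosses over.

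**The case against.** The strongest reply is that grouping harms by allocation is a legitimate choice in a pragmatic trial. Section 10.2.1 uses a treatment-policy strategy for both deviation from treatment and alternative treatment. By-allocation tables match the benefit comparison and keep the protection of randomisation. That stands as a reason to keep such a table. It does not justify making it the only grouping: the estimand is stated for the co-primary outcomes alone, and objective (f) asks about the interventions.

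The SAP, which is not shown, could add a by-treatment-received display without contradicting the protocol. That also stands, but it could not make that display the main safety analysis while 10.1 reads as it does.

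Three stronger readings are tempting and are not supported:
- *That product-specific harm would be hidden.* Causality is judged for each event against the IMP (9.1.3), and expectedness against the reference safety information (9.2, 9.5). Facial weakness has its own examination and ad hoc visit (7.4.4, 7.4.5). Individual cases are not misattributed; only the comparative summaries are affected.
- *That lidocaine and Botox are likely to be swapped because they share sites and volumes.* The trial is open label with central web-based randomisation (7.1.5, 7.2). One product is a vial for reconstitution and the other an ampoule (8.1). Nothing suggests swaps are expected.
- *That the protocol expects TAU participants to move to a trial injectable.* Section 7.6 speaks only of a new TMD therapy. Section 2 makes an injectable possible, but 7.1.2 warns that Botox is unlikely to be immediately available through the NHS after the trial, and 7.9 ties continued injections to local funding.

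**Conclusion.** The point holds as a cheap improvement to the safety analysis. Section 10.1 admits participants by exposure and groups them by allocation. Section 10.2.2 also places the Liverpool profile in ITT, so no stated comparison serves objective (f) by drug received.

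The size depends entirely on how many participants receive a trial drug other than their own, which the protocol does not give. On the assumed 5% one-way crossover and 10% versus 0% event rates, about one event is misplaced and 10 points becomes 9.5. Across the assumed range the loss runs from 1% of the true difference (one-way, c = 1%) to 20% (symmetric, c = 10%). The effect is probably at the small end. The sample size and the efficacy analyses are untouched.

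**What to change.** In section 10.1, state that the Safety Population is analysed according to the trial treatment actually received, and keep the by-allocation table as a supplementary treatment-policy display. In section 10.2.2, leave the Liverpool profile in ITT and add a supplementary display by treatment received; rewording 10.1 alone would not reach it.

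Add a rule for participants exposed to more than one of the trial drugs, and say that this includes a drug obtained in routine care after discontinuation, since otherwise it may not count as trial treatment. Flag the multiple exposure and show those events separately. Assigning each event to the most recent drug is not advisable: section 8.4 allows oral tapers of at least 4 weeks and up to several months, so an event arising during a taper could be charged to a newly started injection. MRI and bone-marker changes, measured only at screening and week 36, have no onset date to which such a rule could apply.

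The cost is one sentence in 10.1, the multiple-exposure rule, an exposure variable from data the CRF already records, and the extra displays. The downside is that the main safety groups are no longer exactly the randomised groups, so differences between them could partly reflect who switched; the retained by-allocation table covers that.

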10.2. Statistical Analyses

The analysis of all outcome measures will be described in detail in a pre-specified Statistical Analysis Plan (SAP) that will be reviewed by the trial's oversight committees and signed off by the CI prior to any comparative analyses being undertaken. Any changes to the statistical analysis plan made afterwards will be documented and reviewed by the senior methodological lead who has not had access to the results of the comparative analyses. Throughout the statistical section (section 10.2), baseline refers to data collected before randomisation at the screening visit.

10.2.1. Analysis of the Co-primary Outcome Measures

The main co-primary objective is to estimate the mean difference in disorder specific quality of life measured by OHIP-TMD and pain intensity measured by CPI at 36 weeks in adults with chronic (≥3months) myalgia temporomandibular disorder (M-TMD) treated with BTX compared to TAU and Lidocaine injections compared to TAU, regardless of deviations from the allocated treatment for any reason. The estimand is described by the following attributes:

Estimand attribute	Description
Population	Adults with chronic (≥3months) myalgia
	temporomandibular disorder (M-TMD)
Treatment conditions	1. BTX injections (intervention)
	2. Lidocaine injections (intervention)
	3. TAU, amitriptyline/gabapentin (control)
Outcome measures	1. Disorder specific quality of life measured by
	OHIP-TMD at 36 weeks
	2. Pain intensity measured by CPI at 36 weeks
Strategies used to handle intercurrent events	1. Deviation from treatment for any reason –
	treatment policy ¹
	2. Initiation of alternative treatments –
	treatment policy ¹
	3. Death – hypothetical ²
Population-level summary measures	1. Mean difference in OHIP-TMD at 36 weeks
	(adjusted for baseline) between each
	intervention and control
	2. Mean difference in CPI at 36 weeks
	(adjusted for baseline) between each
	intervention and control

¹The treatment policy strategy targets the treatment effect regardless of the occurrence of intercurrent event.

The co-primary outcomes of disorder specific quality of life measured by OHIP-TMD, and pain intensity measured by CPI at 36wks will each be compared between treatment groups using separate linear mixed effects regression models with nested random effects for site and participant and fixed effects for treatment, timepoint, treatment by timepoint interaction, baseline score and the stratification factor of psychosocial status. These models will each include the outcome data at all timepoints which will help account for missing data (under a missing at random assumption). These models will each be used to calculate mean differences at 36 weeks (BTX - TAU and Lidocaine injections - TAU) and associated two-sided 95% confidence intervals (CIs) for each coprimary outcome to test the superiority of BTX and Lidocaine injections compared to TAU. Superiority will be concluded if the upper limit of the two-sided 95% CIs are both less than 0. To conclude that BTX or Lidocaine are effective, statistically significant differences in both co-primary outcomes compared to TAU will be needed. This analysis will be conducted in the ITT population.

These models will also each be used to estimate the mean differences (BTX - TAU and Lidocaine injections - TAU) and associated two-sided 95% CIs for the secondary outcomes of disorder specific quality of life measured by OHIP-TMD, and pain intensity measured by CPI at 12 and 24 weeks.

²The hypothetical strategy targets the treatment effect in the hypothetical setting where the intercurrent event would not occur.

A secondary analysis will additionally adjust the estimates for OHIP-TMD by including fixed effects for the baseline covariates of GCPS and duration of pain that are known to be strongly related to outcome. This will also be done for CPI. However, as CPI is a component of the GCPS, baseline GCPS will not be included. We will consider alternative strategies to deal with the intercurrent events of treatment discontinuation and alternative treatments in the SAP.

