10.3. Sample Size Calculations

The sample size will be 663 which has been chosen to provide high power for both the OHIP-TMD and CPI co-primary outcomes (Durham et al., 2021; Dworkin et al., 2008; Yule et al., 2015; Collignon et al., 2020).

From Yule et al, the standard deviation (SD) of OHIP-TMD is 20.7 at 12 weeks (Yule et al., 2015), which we expect to be consistent at subsequent measurement times. The correlation with baseline was 0.6. To have 90% power (two-sided 5% type I error rate) to detect a difference between arms equal to the minimally important clinical difference (MICD) of 6.0 would require 251 per arm; taking the correlation into account would reduce this to $(1-0.6^2)*251 = 161$ per arm. We have inflated this by 27% to account for worst-case scenario loss-to-follow up identified between two large research studies we have conducted involving treatment and M-TMD (Durham et al., 2021; Yule et al., 2015). This gives a required sample size of 663.

This sample size provides extremely high power (>99%) to detect differences between arms in the CPI, which we assume has an SD of 20 based on the DEEP study (Durham et al., 2021) and MICD of 10 (Dworkin et al., 2008). To conclude superiority, statistically significant differences in both OHIP-TMD and CPI will be needed, meaning that an adjustment for multiple testing is not required and that the overall power is approximately 90% for each separate comparison (BTX vs TAU and Lidocaine vs TAU). As per consensus on multi-arm trials with distinct interventions, we do not formally adjust for multiple intervention arms (Collignon et al., 2020), but the total chance of recommending an ineffective intervention as superior to TAU is <5%. The quantity and timing of attrition will be monitored. If the attrition rate by 36 weeks increases above the estimated 27%, we may increase the sample size to maintain the power of the trial in agreement with the trial's oversight committees and subject to funding and time constraints.

11. Economic Analysis

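### The co-primary model, read literally, gives correct week-36 confidence intervals only if variance and baseline correlation stay stable across visits; a visit-specific covariance removes that dependence at no cost

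*Protocol*

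**What the plan says.** Section 10.2.1 specifies "separate linear mixed effects regression models with nested random effects for site and participant and fixed effects for treatment, timepoint, treatment by timepoint interaction". The fixed-effect list ends with "treatment by timepoint interaction, baseline score and the stratification factor of psychosocial status". There is therefore one baseline effect, common to all visits, and no baseline-by-timepoint term. No residual covariance structure is named.

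The model uses every post-baseline visit: "These models will each include the outcome data at all timepoints which will help account for missing data (under a missing at random assumption"). The decision is taken at week 36: "Superiority will be concluded if the upper limit of the two-sided 95% CIs are both less than 0", and an intervention must succeed on both OHIP-TMD and CPI.

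Section 10.3 plans on an OHIP-TMD SD of 20.7 at 12 weeks, expected to hold at later visits, and adds: "The correlation with baseline was 0.6". It gives no separate value for week 36. It also states that "the total chance of recommending an ineffective intervention as superior to TAU is <5" per cent. Section 10.2 leaves the detailed description of the analyses to the SAP.

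**The concern.** Random intercepts for site and participant with independent residuals imply one variance at all three visits and one correlation between any two visits. A single baseline slope implies that baseline predicts week 36 as strongly as week 12. Under these constraints the week-36 standard error is partly borrowed from the earlier visits.

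A weaker link with baseline at week 36 is plausible. Week 36 is three times as far from baseline as week 12. Under the treatment-policy strategy, scores after discontinuation or a new therapy are kept, and such events accumulate with time. If the link weakens while the SD stays the same, residual variance at week 36 exceeds the pooled value and the interval that decides the trial is too narrow. The same covariance also governs how missing week-36 values are inferred from earlier visits, with up to 27% loss planned for. No bias from that route has been quantified here.

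**Working it through.** **Inputs from section 10.3.** SD 20.7, difference 6.0, baseline correlation 0.6, two-sided 5%, 90% power, 27% loss, 663 in total (221 per arm).

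**The plan's own figures.** n per arm = 2 × (1.960 + 1.2816)² × 20.7² / 6.0² = 250.1, so 251. Then 251 × (1 − 0.6²) = 160.6, so 161. Then 161 / 0.73 = 220.5, so 221, and 3 × 221 = 663. All are reproduced.

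**The under-5% statement.** Take an arm that truly works on one co-primary and is null on the other, which is the least favourable case. The error is then that of two favourable 2.5% tests sharing one control (correlation 0.5 between the test statistics). Their union is 4.54%, so the statement is reproduced when standard errors are correct.

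**Closed form, complete data.** Take a baseline SD of 20.7 (assumed). With constant SD and baseline correlations r₁, r₂, r₃ at weeks 12, 24 and 36, the common slope is b = mean(r). The residual variance at visit j, in units of 20.7², is v_j = 1 − 2b·r_j + b². The model uses mean(v), but the truth at week 36 is v₃. The ratio of true to model SE is k = √(v₃ / mean(v)), and the two-sided error is 2Φ(−1.96/k).

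Worked case 0.6/0.5/0.4: b = 0.5 and v = 0.65, 0.75, 0.85, with mean 0.75. So k = √(0.85/0.75) = 1.065, two-sided error is 6.6% and the union is 5.9%.

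| Baseline correlation | SD by visit | k | Two-sided error | Union |
|---|---|---|---|---|
| 0.6/0.6/0.6 | 20.7 throughout | 1.000 | 5.0% | 4.5% |
| 0.6/0.575/0.55 | 20.7 throughout | 1.021 | 5.5% | 5.0% |
| 0.6/0.55/0.5 | 20.7 throughout | 1.039 | 5.9% | 5.3% |
| 0.6/0.5/0.4 | 20.7 throughout | 1.065 | 6.6% | 5.9% |
| 0.6/0.5/0.4 | 20.7/20/19 (assumed) | 1.021 | 5.5% | 5.0% |
| 0.6/0.6/0.6 | 20.7/20/19 (assumed) | 0.954 | 4.0% | 3.7% |

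For the last two rows v_j = s_j² − 2b·r_j·s_j + b², with s_j = SD_j/20.7 and b = mean(r_j·s_j). Break-even for 5% overall is k of about 1.02, which at constant SD is a week-36 correlation of about 0.55.

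**With attrition.** Further assumptions are 221 per arm, retention 88/80/73% (monotone), SD 20.7, and correlations of 0.75 between adjacent visits and 0.65 between weeks 12 and 36. The model-based and true (sandwich) variances of the week-36 contrast were compared. The last column is the SE from an unstructured covariance with baseline-by-visit terms.

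| Baseline correlation | Model SE | True SE | SE too small by | Two-sided error | Union | Unstructured SE |
|---|---|---|---|---|---|---|
| 0.6/0.6/0.6 | 1.787 | 1.800 | 0.7% | 5.2% | 4.7% | 1.797 |
| 0.6/0.55/0.5 | 1.852 | 1.943 | 4.7% | 6.2% | 5.5% | 1.935 |
| 0.6/0.5/0.4 | 1.910 | 2.058 | 7.2% | 6.9% | 6.2% | 2.037 |
| 0.6/0.5/0.35 | 1.927 | 2.110 | 8.7% | 7.4% | 6.6% | 2.076 |

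**Simulation.** REML fits with 663 participants, 27% random dropout, no site variance and assumed visit correlations of 0.55-0.70 agree. Correlations of 0.6/0.55/0.5, 0.6/0.5/0.4 and 0.6/0.45/0.3 gave SE ratios of 1.05, 1.08 and 1.09. Two-sided errors were 6.0%, 7.1% and 7.4%, and unions 5.1%, 5.9% and 7.0%, with Monte Carlo error of 0.3-0.4 points. The unstructured model gave two-sided errors of 4.9-5.8%, consistent with 5% given its larger Monte Carlo error of 0.5-0.7 points.

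**Arm null on both outcomes.** With between-outcome correlation of 0.3-0.7, the overall error is 0.5-1.6% at k = 1.0 and 0.9-2.5% at k = 1.10.

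**The case against.** The strongest reply is that the protocol does not literally impose equal variances and correlations. It names random effects, does not say they are intercepts only, is silent on the residuals and leaves detail to an SAP that is not shown. An unstructured residual could still be specified there. This stands for the residual covariance. It stands less well for the baseline term, because the fixed effects are listed one by one and an SAP that follows the list has a single slope.

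Secondly, every unfavourable figure rests on inputs the protocol does not give: the week-36 correlation, the between-visit correlations and the timing of attrition. All of those scenarios hold SD constant and move the correlation down. The SD rows above show that a modest fall in SD brings the result back to break-even or makes the intervals too wide. This also stands.

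A reader might infer that the stated under-5% error rate is wrong. The documents do not support that. On constant SD and a correlation of 0.6 the model is essentially calibrated and the statement reproduces. A breach needs both a drift over visits and an arm that works on one co-primary but not the other. The mildest simulated breach, 5.1%, cannot be told apart from 5%.

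**Conclusion.** The point holds as a conditional weakness with a free remedy. Read as random intercepts with independent residuals and one baseline slope, the model is valid at week 36 only if variance and baseline correlation are stable over visits. The protocol asserts the first and gives no week-36 figure for the second. If the correlation fades to between 0.5 and 0.35 at constant SD, week-36 standard errors are about 5-9% too small. Two-sided error is then about 6-7.4%, and the total chance about 5.5-6.6% for an arm effective on CPI and null on OHIP-TMD. For an arm null on both outcomes the bound holds easily. The direction depends on how the SD behaves, which the documents do not settle. The case for change is that the alternative stays valid whichever way variance or correlation drifts. Its week-36 SE was no larger than the stated model's true SE in any attrition scenario calculated.

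**What to change.** In section 10.2.1 or the SAP, before any comparative analysis:

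- Replace the participant random intercept with an unstructured, visit-specific residual covariance for weeks 12, 24 and 36.
- Add a baseline-by-timepoint interaction.
- Keep site as a random effect and the PHQ-4 stratum as a fixed effect.
- Name a fallback if the model does not converge, such as heterogeneous compound symmetry.
- Use the same form only for secondary outcomes measured at baseline and at all three visits (PHQ-4, BPSQI, SF-JFLS). It does not suit GIC or LAEP, which the schedule of events does not collect at screening, or FaCE, which is completed only when a participant perceives facial weakness.

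Small-sample degrees of freedom are optional with 663 participants. The cost is a few sentences and a few extra parameters. The data collected, sample size and estimand do not change.
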